6.2 Criteria to Restart Nintedanib

A patient is eligible to restart nintedanib if all criteria listed in the table below are met.

If a patient has to interrupt intake of nintedanib due to an adverse event for more than 14 days, the decision to restart treatment with nintedanib needs to be discussed and agreed upon between the investigator and the study supporter.

All criteria have to be met in order to restart nintedanib

- nausea CTCAE grade ≤ 2
- vomiting CTCAE grade ≤ 1
- diarrhoea CTCAE grade < 2
- AST and ALT CTCAE grade ≤ 2 and bilirubin CTCAE grade ≤ 1
- no other non-hematological adverse event grade CTCAE ≥ 3 which is considered drug-related

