1.6 Benefit – Risk Assessment

Although considerable progress has occurred in understanding the biological characteristics of cancer as well as the development of more effective treatment regimens, most patients with locally advanced or metastatic tumors succumb to their disease. Thus, there is a substantial need for novel therapeutic strategies to improve the outcome for patients with advanced or metastatic non-small cell lung cancer.

Antiangiogenic treatment with the orally available triple angiokinase inhibitor nintedanib (BIBF1120) with inhibition of VEGFR, PDGFR, RET and FGFR offers the chance to control both locally recurrent and distant metastatic disease on an outpatient basis. Treatment with nintedanib (BIBF1120) may have the potential to provide significant benefit to patients with locally advanced and/or metastatic non-small cell lung cancer by slowing tumor progression and metastasis, since its cellular target is expressed on the tumor vasculature in most malignancies. Induction of endothelial cell apoptosis may result in subsequent degradation of tumor vessels and subsequent tumor necrosis. Additionally, tumor growth may be affected by direct anti-tumour effects, e.g. tumor cells that express VEGFR, PDGFR, RET, or FGFR.

The risks of therapy with nintedanib (BIBF1120) in adult patients are primarily related to:

- the gastro-intestinal tract (nausea, vomiting, diarrhea, abdominal pain)
- increases in liver enzymes (AST, ALT, γ-GT)
- fatigue, asthenia and anorexia.

Liver enzymes must be followed closely during treatment with nintedanib (BIBF1120).

Therapy with the trial drugs must be interrupted in the event of relevant hepatic toxicity and further treatment is to be withheld until recovery of the abnormal laboratory parameters.

Protocol Version: 02/02/24 Page 15 of 57

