6.0 DOSE DELAYS/DOSE MODIFICATIONS

6.1 Criteria for Interruption of Treatment with Nintedanib

Treatment with nintedanib has to be interrupted in case any of the criteria listed in the table below is fulfilled.

Protocol Version: 02/02/24 Page 22 of 57

If one criterion is met, nintedanib has to be interrupted

- nausea of CTCAE grade ≥ 3 despite supportive care
- vomiting of CTCAE grade ≥ 2 despite supportive care
- diarrhea of CTCAE grade ≥ 2 for more than 3 consecutive days despite supportive care
- AST and/or ALT of CTCAE grade ≥ 2 in conjunction with bilirubin of CTCAE grade ≥ 1
- AST and/or ALT of CTCAE grade ≥ 3
- other non-hematological adverse event of CTCAE grade ≥ 3 considered drugrelated

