6.3 Dose Adjustments of Nintedanib

As initial measure for the management of side effects, treatment with nintedanib should be temporarily interrupted until the specific adverse reaction has resolved to levels that allow continuation of therapy. Nintedanib treatment may be resumed at a reduced dose. Dose adjustments in 100 mg steps per day (i.e. a 50 mg reduction per dosing) based on individual safety and tolerability are recommended as described in the sections above. In case of further persistence of the adverse reaction(s), i.e. if a patient does not tolerate 100 mg twice daily, treatment with nintedanib should be discontinued.

The following dose levels will be used in case dose adjustments are required for management of undue toxicity.

Protocol Version: 02/02/24 Page 23 of 57

Dose-level:	0	-1	-2	-3
Dose:	200 mg BID	150 mg BID	100 mg BID	Discontinue

Of note:

If the dose of nintedanib had to be reduced due to toxicity, it will stay on the lower dose level for the entire time of administration.

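### The liver restart row in section 6.2 is met at AST/ALT grade 2 with bilirubin grade 1, a result at which section 6.1 requires nintedanib to be interrupted

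*Combined protocol and SAP*

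**What the plan says.** Section 6.1 lists the reasons to stop, under the rule "If one criterion is met, nintedanib has to be interrupted". Two items concern the liver: AST and/or ALT of grade 3 or higher, and "AST and/or ALT of CTCAE grade ≥ 2 in conjunction with bilirubin of CTCAE grade ≥ 1".

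Section 6.2 governs restarting: "A patient is eligible to restart nintedanib if all criteria listed in the table below are met". Its table has one liver row, "AST and ALT CTCAE grade ≤ 2 and bilirubin CTCAE grade ≤ 1". The investigator and the study supporter must agree on a restart only in the case described as "If a patient has to interrupt intake of nintedanib due to an adverse event for more than 14 days". For shorter interruptions the table is the only specific check.

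Two other places describe the intent in general terms. Section 1.6 says that after relevant hepatic toxicity "further treatment is to be withheld until recovery of the abnormal laboratory parameters". Section 6.3 says that "treatment with nintedanib should be temporarily interrupted until the specific adverse reaction has resolved to levels that allow continuation of therapy". Neither gives a liver grade.

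**The concern.** A restart rule should require the patient to be outside the state that caused the stop. Here the stop rule and the restart rule share a state. At AST/ALT grade 2 with bilirubin grade 1, a single blood draw obliges the investigator to stop the drug and also meets the liver condition for giving it again.

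What is at stake is re-exposure before recovery in patients whose enzymes and bilirubin are raised together. The protocol treats the liver as a main risk: section 1.3.2 names reversible enzyme elevations as the principal dose-limiting toxicity, and section 1.6 asks for close follow-up of liver enzymes. An investigator who follows the section 6.2 table for a short interruption could restart at a level where section 6.1 requires the drug to be stopped again.

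**Working it through.** The plan states no figure to reproduce. The check sets the two tables side by side and lists every grade combination.

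**Inputs**

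- Let A be the worse of the AST and ALT grades, and B the bilirubin grade, each from 0 to 4. Using the worse grade is right for both rules, because section 6.1 is triggered by either enzyme and section 6.2 requires both to be low enough.
- Stop, liver items of section 6.1: (A ≥ 2 and B ≥ 1) or A ≥ 3.
- Restart, liver row of section 6.2: A ≤ 2 and B ≤ 1.

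**Grid** (S = stop required, R = liver restart row met, – = neither)

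| A | B = 0 | B = 1 | B = 2 | B = 3 | B = 4 |
|---|---|---|---|---|---|
| 0 | R | R | – | – | – |
| 1 | R | R | – | – | – |
| 2 | R | **S and R** | S | S | S |
| 3 | S | S | S | S | S |
| 4 | S | S | S | S | S |

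**Counts**

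- Stop: 3 × 4 = 12 pairs with A ≥ 2 and B ≥ 1, plus 2 pairs with A ≥ 3 and B = 0, giving 14.
- Restart: 3 × 2 = 6.
- Both: A ≥ 2 with A ≤ 2, and B ≥ 1 with B ≤ 1, leaves only A = 2, B = 1. That is 1 pair.
- Stop pairs that need some improvement before the liver row is met: 14 − 1 = 13. For these the row still allows a restart on reaching (2, 1), which is itself a stop pair.

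**Other rows, same test**

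| Row | Section 6.1 stops at | Section 6.2 restarts at | Grades in both |
|---|---|---|---|
| Nausea | ≥ 3 | ≤ 2 | 0 |
| Vomiting | ≥ 2 | ≤ 1 | 0 |
| Diarrhea | ≥ 2 | < 2 | 0 |
| Other non-hematological, drug-related | ≥ 3 | none ≥ 3 | 0 |

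This leaves out the duration and supportive-care qualifiers in section 6.1. They only narrow the stop rules, so they cannot create an overlap. The liver row is the only one that overlaps.

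**After the fix**

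Adding the condition that no liver criterion in section 6.1 is met removes (2, 1) from the restart set. Five pairs remain: (0,0), (0,1), (1,0), (1,1) and (2,0). None of them is a stop pair.

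**The case against.** The strongest reply is that section 6, read as a whole, already forbids this restart. Section 6.1 is mandatory and is not confined to first exposure. Section 6.2 only makes a patient eligible. Section 6.3 holds the drug until the reaction has settled to a level compatible with continuing, and a level at which section 6.1 compels a stop is not such a level. This limits the practical harm, and a careful investigator would reach that reading. It does not remove the conflict. Section 6.3 sets no liver level of its own, section 6.2 is the only place where one is given, and the level given there contradicts section 6.1. That the drug would have to be stopped again confirms the contradiction.

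A second reply is that the patient may return on a lower dose. Section 6.3 permits this, and section 6.4 requires a reduction when the event is drug-related. But section 6.1 has no exception for a reduced dose, so the same values require a stop at any dose.

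A reader might also infer more than the documents support:

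- *That the liver row asks for no recovery at all.* This is true of 1 of the 14 stop pairs. The other 13 need some improvement.
- *That one unresolved event would use up the dose ladder.* Reductions are permanent ("it will stay on the lower dose level for the entire time of administration") and section 6.4 stops treatment at the third episode. But an episode is not defined, and section 6.3 itself foresees stepping down, and finally stopping, when a reaction persists. This is at most a possible side effect.
- *That follow-up of liver events of special interest is undermined.* Section 7.6.2 ties the end of that follow-up to the retreatment criteria, so the row bears only on when follow-up may end. Appendix C separately requires repeat testing within 48 hours and then at least weekly.
- *That the special-interest thresholds, given as multiples of the upper limit of normal, disagree with the graded stop rules.* The documents do not print the CTCAE cut-offs, so they cannot show this.

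**Conclusion.** The point holds as an internal inconsistency at one grade pair, AST/ALT grade 2 with bilirubin grade 1. It rests only on the two tables as printed and needs no outside figure. It looks like a drafting slip, because the other four rows are consistent with their stop rules and sections 1.6 and 6.3 both call for recovery.

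The number of patients affected cannot be derived. Twenty are planned, and section 1.3.2 reports that bilirubin seldom rose together with the enzymes, so few would be expected. The severity is minor: a safety correction with no effect on the primary response analysis.

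**What to change.** Add to the liver row of section 6.2: *and no liver criterion in 6.1 is met*. Equivalent wording in grades is: AST and ALT grade ≤ 1 with bilirubin grade ≤ 1, or AST and ALT grade ≤ 2 with bilirubin grade 0. Both versions give the same five restart pairs. Neither changes a threshold in section 6.1. Restart at AST/ALT grade 2 with normal bilirubin stays possible, which is right because section 6.1 does not require a stop there.

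The change is one clause in one table row, with no added scheduled visits or patients. The downside is an occasional longer interruption while AST/ALT falls to grade 1 or bilirubin to grade 0. This may bear more on patients who enter with raised liver values, since section 3.1 allows higher AST/ALT when liver metastases are present. The documents do not allow the extra time to be estimated. Some of these interruptions may pass 14 days and then need the discussion that section 6.2 already requires.

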6.3 Dose Adjustments of Nintedanib

As initial measure for the management of side effects, treatment with nintedanib should be temporarily interrupted until the specific adverse reaction has resolved to levels that allow continuation of therapy. Nintedanib treatment may be resumed at a reduced dose. Dose adjustments in 100 mg steps per day (i.e. a 50 mg reduction per dosing) based on individual safety and tolerability are recommended as described in the sections above. In case of further persistence of the adverse reaction(s), i.e. if a patient does not tolerate 100 mg twice daily, treatment with nintedanib should be discontinued.

The following dose levels will be used in case dose adjustments are required for management of undue toxicity.

Protocol Version: 02/02/24 Page 23 of 57

Dose-level:	0	-1	-2	-3
Dose:	200 mg BID	150 mg BID	100 mg BID	Discontinue

Of note:

If the dose of nintedanib had to be reduced due to toxicity, it will stay on the lower dose level for the entire time of administration.

6.4 Management of Adverse Events

CTCAE Adverse reaction	Dose adjustment
Diarrhea ≥ grade 2 for more than 7 consecutive days	
despite anti-diarrheal treatment	
OR	
diarrhoea ≥ grade 3 despite anti-diarrheal treatment	1st episode
Vomiting \geq grade 2	Reduce dose from 200 mg
AND/OR	twice daily to 150 mg twice
Nausea ≥ grade 3 despite anti-emetic treatment	daily
AST and/or ALT elevations grade 2 in conjunction	
with bilirubin of \geq grade 1	2nd episode
OR	Reduce dose from 150 mg
AST and/or ALT elevations of \geq grade 3	twice daily to 100 mg twice
Other non-hematological or hematological adverse	daily
reaction of \geq grade 3	
	3rd episode
	Stop treatment

Please note, dose adjustments are only required in adverse events that are drug-related.

If nintedanib will be combined with compounds that are solely metabolized by the liver and / or induce liver enzyme elevations, both molecules should be reduced in case of liver enzyme elevations according to the defined dose reductions for nintedanib as mentioned above and for the other compound as mentioned in their prescribing information.

7.0 REGULATORY AND REPORTING REQUIREMENTS

The entities providing oversight of safety and compliance with the protocol require reporting as outline below.

The Washington University Human Research Protection Office (HRPO) requires that all events meeting the definition of unanticipated problem or serious noncompliance be reported as outlined in Section 7.2.

Protocol Version: 02/02/24 Page 24 of 57

Boehringer Ingelheim and NCCN require that all events as defined in Section 7.6 be reported as outlined.

7.1 Definitions

7.1.1 Adverse Events (AEs)

Definition: any unfavorable medical occurrence in a human subject including any abnormal sign, symptom, or disease.

Grading: the descriptions and grading scales found in the revised NCI Common Terminology Criteria for Adverse Events (CTCAE) version 4.0 will be utilized for all toxicity reporting. A copy of the CTCAE version 4.0 can be downloaded from the CTEP website.

Attribution (relatedness), Expectedness, and Seriousness: the definitions for the terms listed that should be used are those provided by the Department of Health and Human Services' Office for Human Research Protections (OHRP). A copy of this guidance can be found on OHRP's website:

http://www.hhs.gov/ohrp/policy/advevntguid.html

7.1.2 Serious Adverse Event (SAE)

Definition: any adverse drug experience occurring at any dose that results in any of the following outcomes:

- o Death
- o A life-threatening adverse drug experience
- o Inpatient hospitalization or prolongation of existing hospitalization
- A persistent or significant disability/incapacity (i.e., a substantial disruption of a person's ability to conduct normal life functions)
- o A congenital anomaly/birth defect
- Any other experience which, based upon appropriate medical judgment, may jeopardize the subject and may require medical or surgical intervention to prevent one of the outcomes listed above

7.1.3 Unexpected Adverse Experience

Definition: any adverse drug experience, the specificity or severity of which is not consistent with the current investigator brochure (or risk information, if an IB is not required or available).

7.1.4 Life-Threatening Adverse Experience

Definition: any adverse drug experience that places the subject (in the view of the investigator) at immediate risk of death from the reaction as it occurred, i.e., it does

Protocol Version: 02/02/24 Page 25 of 57

not include a reaction that, had it occurred in a more severe form, might have caused death.

7.1.5 Unanticipated Problems

Definition:

- unexpected (in terms of nature, severity, or frequency) given (a) the research procedures that are described in the protocol-related documents, such as the IRB-approved research protocol and informed consent document; and (b) the characteristics of the subject population being studied;
- related or possibly related to participation in the research ("possibly related"
 means there is a reasonable possibility that the incident, experience, or
 outcome may have been caused by the procedures involved in the research);
 and
- suggests that the research places subjects or others at a greater risk of harm (including physical, psychological, economic, or social harm) than was previously known or recognized.

7.1.6 Noncompliance

Definition: failure to follow any applicable regulation or institutional policies that govern human subjects research or failure to follow the determinations of the IRB. Noncompliance may occur due to lack of knowledge or due to deliberate choice to ignore regulations, institutional policies, or determinations of the IRB.

7.1.7 Serious Noncompliance

Definition: noncompliance that materially increases risks, that results in substantial harm to subjects or others, or that materially compromises the rights or welfare of participants.

7.1.8 Protocol Exceptions

Definition: A planned deviation from the approved protocol that are under the research team's control. Exceptions apply only to a single participant or a singular situation.

Pre-approval of all protocol exceptions must be obtained prior to the event.

7.2 Reporting to the Human Research Protection Office (HRPO) at Washington University

The PI is required to promptly notify the IRB of the following events:

Protocol Version: 02/02/24 Page 26 of 57

- Any unanticipated problems involving risks to participants or others which occur at WU, any BJH or SLCH institution, or that impacts participants or the conduct of the study.
- Noncompliance with federal regulations or the requirements or determinations of the IRB.
- Receipt of new information that may impact the willingness of participants to participate or continue participation in the research study.

These events must be reported to the IRB within 10 working days of the occurrence of the event or notification to the PI of the event. The death of a research participant that qualifies as a reportable event should be reported within 1 working day of the occurrence of the event or notification to the PI of the event.

7.3 Reporting to the Quality Assurance and Safety Monitoring Committee (QASMC) at Washington University

The PI is required to notify the QASMC of any unanticipated problem occurring at WU or any BJH or SLCH institution that has been reported to and acknowledged by HRPO as reportable. (Unanticipated problems reported to HRPO and withdrawn during the review process need not be reported to QASMC.)

QASMC must be notified within **10 days** of receipt of IRB acknowledgment via email to a QASMC auditor.

7.4 Reporting Requirements for Secondary Sites

The research team at each secondary site is required to promptly notify the Washington University PI and research coordinator of all reportable events (as described in Section 7.6) within 1 working day of the occurrence of the event or notification of the secondary site's PI of the event. This notification may take place via email if there is not yet enough information for a formal written report (using either an FDA MedWatch form if required or an institutional SAE reporting form if not). A formal written report must be sent to the Washington University PI and research coordinator within 10 working days of the occurrence of the event or notification of the secondary site's PI of the event. The death of a research participant that qualifies as a reportable event should be reported within 1 working day of the occurrence of the event or notification of the secondary site's PI of the event.

The research team at a secondary site is responsible for following its site's guidelines for reporting applicable events to its site's IRB according to its own institutional guidelines.

7.5 Reporting to Secondary Sites

The Washington University PI (or designee) will notify the research team at each secondary site of all reportable events that have occurred at other sites within 10 working days of the

Protocol Version: 02/02/24 Page 27 of 57

occurrence of the event or notification of the PI of the event. This includes events that take place both at Washington University and at other secondary sites, if applicable.

7.6 Reporting to Boehringer Ingelheim and NCCN

7.6.1 Definitions

Adverse event

An adverse event (AE) is defined as any untoward medical occurrence, including an exacerbation of a pre-existing condition, in a patient in a clinical investigation who received a pharmaceutical product. The event does not necessarily have to have a causal relationship with this treatment.

Serious adverse event

A serious adverse event (SAE) is defined as any AE which results in death, is immediately life-threatening, results in persistent or significant disability / incapacity, requires or prolongs patient hospitalisation, is a congenital anomaly / birth defect, or is to be deemed serious for any other reason if it is an important medical event when based upon appropriate medical judgement which may jeopardise the patient and may require medical or surgical intervention to prevent one of the other outcomes listed in the above definitions.

Patients may be hospitalised for administrative or social reasons during the trial (e.g. days on which infusion takes place, long distance from home to site...). These and other hospitalisations planned at the beginning of the trial do not need to be reported as an SAE.

Severity of adverse event

The severity of the AE should be judged based on the following:

The severity of adverse events should be classified and recorded according to the Common Terminology Criteria for Adverse Events (CTCAE) <add version> in the (e)CRF.

Causal relationship of adverse event

Medical judgment should be used to determine the relationship, considering all relevant factors, including pattern of reaction, temporal relationship, de-challenge or re-challenge, confounding factors such as concomitant medication, concomitant diseases and relevant history. Assessment of causal relationship must be recorded for each adverse event.

Causality will be reported as either "Yes" or "No".

Yes: There is a reasonable causal relationship between the investigational product administered and the AE.

Protocol Version: 02/02/24 Page 28 of 57

No: There is no reasonable causal relationship between the investigational product administered and the AE.

Worsening of the underlying disease or other pre-existing conditions

Worsening of the underlying disease or of other pre-existing conditions will be recorded as an AE in the CRF.

Changes in vital signs, ECG, physical examination, and laboratory test results Changes in vital signs, ECG, physical examination and laboratory test results will be recorded as an AE in the CRF, if they are judged clinically relevant by the investigator.

7.6.2 Adverse Events of Special Interests (AESI)

The following events are considered as protocol-specified events of special interests:

Any gastrointestinal- and non-gastrointestinal perforation, leakage, fistula formation, abscess

In such case the following additional information need to be collected, documented in the respective comment field of the CRF page and the respective narratives of the SAE. That has to be forwarded to Boehringer Ingelheim:

- Location of perforation, leakage, fistula, abscess
- Location/extent of abdominal tumor manifestations,
- Imaging & reports (CT, ultrasound, endoscopy, pathology, etc.)
- Prior surgery (location, wound healing complications)
- Concomitant diseases with GI involvement (e.g., M Crohn, vasculitis, tuberculosis, diverticulitis)
- Thromboembolic events (or predisposition)

Drug-induced liver injury is under constant surveillance by sponsors and regulators and is considered a protocol-specified adverse event of special interest (AESI). Timely detection, evaluation, and follow-up of laboratory alterations of selected liver laboratory parameters to distinguish an effect of the investigational drug from other causes are important for patient safety and for the medical and scientific interpretation of the finding.

The following are considered as protocol-specified AESI:

- An elevation of ALT and / or AST > 5x ULN without bilirubin elevation measured in the same blood draw sample
- An elevation of AST and/or ALT >2.5 fold ULN combined with an elevation of bilirubin to >1.5 fold ULN measured in the same blood draw sample

Protocol Version: 02/02/24 Page 29 of 57

Patients showing above laboratory abnormalities need to be followed up until the protocol specific retreatment criteria have been met and according to Appendix C of this clinical trial protocol.

Protocol-specified AESI are to be reported in an expedited manner similar to Serious Adverse Events, even if they do not meet any of the seriousness criteria.

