The US-FDA has published a Guidance for Industry entitled, "Drug-Induced Liver Injury: Premarketing Clinical Evaluation" which outlines the detection, evaluation, follow-up and reporting of drug-induced liver injury in clinical trials. Drugs that have the potential for inducing severe liver injury may be identified by marked peak aminotransferase elevations (10x-, 15xULN), or the combination of hepatocellular injury (aminotransferase elevation ≥3xULN) and altered liver function (hyperbilirubinemia ≥2xULN) which is defined as potential "Hy's law case" if not explained by other causes including evidence of biliary obstruction (i.e., significant elevation of alkaline phosphatase, ALP, >2X ULN) or some other explanation of the injury (e.g., viral hepatitis, alcohol hepatitis, concomitant use of other known hepatotoxic drugs). This constellation predicts a poor outcome and although very rare, these potential cases have to be well characterized as soon as being identified as other confounding conditions may be the cause.

In further consideration of this FDA Guidance, any potential "Hy's Law case" has to be reported in an expedited manner to the FDA (i.e., even before all other possible causes of liver injury have been excluded) and be followed-up appropriately. The follow-up includes a detailed clinical evaluation and identification of possible alternative etiologies for the "Hy's Law case" constellation such as concomitant diseases (e.g. Hepatitis B) and/or other concomitant therapies that might potentially be hepatotoxic.

Although rare, a potential for drug-induced liver injury is under constant surveillance by sponsors and regulators. Therefore, this study requires timely detection, evaluation, and follow-up of laboratory alterations of selected liver laboratory parameters to ensure patients' safety.

The concept below has been worked out by Boehringer Ingelheim (BI) in order to guard patient's safety and to respond to regulatory requirements. It is the basis for all clinical studies and should be applied as appropriate.

Defintion

The following changes in the laboratory values are considered to be a protocol-specific significant adverse event for all patients with normal values for ALT/AST at baseline:

Protocol Version: 02/02/24 Page 50 of 57

- an elevation of ALT and / or AST > 5x ULN without bilirubin elevation measured in the same blood draw sample

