- an elevation of AST and/or ALT >2.5 fold ULN combined with an elevation of bilirubin to >1.5 fold ULN measured in the same blood draw sample.

These definitions are in line with the current dose reduction recommendations as outlined in all study protocols for BIBF 1120.

Patients showing these laboratory abnormalities need to be followed up until the protocol specific retreatment criteria have been met

For patients with elevated ALT/AST values at baseline special considerations apply, if they are eligible for inclusion into the trial, e.g. if liver metastasis are present and do not qualify as exclusion criterion. For those special cases the BI contact person should be involved.

Procedures

- 1. Protocol-specified significant events are to be reported in an expedited manner similar as Serious Adverse Events, even if they do not meet any of the seriousness criteria and documented in the eCRF
- 2. Replication of the following laboratory tests for confirmation within 48 hours:
 - AST, ALT,
 - bilirubin measurement (total and direct bilirubin)
 - Alkaline Phosphatase
 - Haptoglobin
 - Complete blood count and cell morphology
 - Reticulocyte count
 - CK
 - LDH

The results of these repeated laboratory tests must be documented on the eCRF /CRF forms and reported immediately via the SAE form to BI.

- 3. An evaluation of the patient within 48 hours with respect to but not limited to:
 - Abdominal ultrasound or clinically appropriate other imaging and investigations adequate to rule out biliary tract, pancreatic, intra- or extrahepatic pathology, e.g. bile duct stones, neoplasm, hepatic tumour involvement, biliary tract, pancreatic or intrahepatic pathology, vascular hepatic conditions such as portal vein thrombosis or right heart failure. These data need to be collected, documented in the respective field of the eCRF / CRF / additional documentation form, and the respective SAE form has to be updated and forwarded to BI

Protocol Version: 02/02/24 Page 51 of 57

- detailed history of current symptoms and concurrent diagnoses and medical history
- detailed history of concomitant drug use (including non-prescription medications, herbal and dietary supplement preparations and eg steroids as concomittant suppportive treatment), alcohol use, recreational drug use, and special diets detailed history of exposure to environmental chemical agents

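### Read literally, the two laboratory AESI criteria miss ALT/AST above 5x ULN when bilirubin is above 1.0 and up to 1.5x ULN, so the automatic expedited report and 48-hour work-up are lost

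*Combined protocol and SAP*

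**What the plan says.** Section 7.6.2 lists two laboratory findings that count as protocol-specified AESIs. The first is "An elevation of ALT and / or AST > 5x ULN without bilirubin elevation measured in the same blood draw sample". The second is "An elevation of AST and/or ALT >2.5 fold ULN combined with an elevation of bilirubin to >1.5 fold ULN", again in the same sample. The first gives no figure for what counts as a bilirubin elevation.

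Meeting either one has two consequences. Section 7.6.2 states that "Protocol-specified AESI are to be reported in an expedited manner similar to Serious Adverse Events", even if the event is not serious. Follow-up then runs under Appendix C, which requires repeat laboratory tests and an evaluation of the patient, each within 48 hours.

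The Definition part of Appendix C repeats both criteria, the first as "an elevation of ALT and / or AST > 5x ULN without bilirubin elevation measured in the same blood draw sample". It restricts them to patients with normal ALT/AST at baseline, a restriction that 7.6.2 does not carry. It then adds: "These definitions are in line with the current dose reduction recommendations".

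The dosing rules handle bilirubin differently. Section 6.1 interrupts nintedanib for "AST and/or ALT of CTCAE grade ≥ 3", with no bilirubin condition, and has a separate rule for a lower enzyme grade combined with raised bilirubin. Section 6.4 has the same structure for dose reduction.

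**The concern.** The two criteria look as if they were meant to divide all large enzyme rises between them: one for a normal bilirubin, one for a raised bilirubin. They do not meet. If an elevation means any value above ULN, the first criterion stops at 1.0x ULN and the second starts above 1.5x ULN.

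The consequence runs the wrong way. ALT at 6x ULN with normal bilirubin is an AESI. ALT at 20x ULN with bilirubin at 1.3x ULN is not, although both liver measures are abnormal.

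Eligible patients can start inside the band, because inclusion criterion 8g admits total bilirubin up to 1.5x IULN. On this reading, a patient whose bilirubin stays at 1.2x ULN can meet neither criterion at any ALT/AST level.

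At stake are the automatic expedited report and the 48-hour work-up for a hepatotoxicity signal, with a drug whose dose-limiting toxicity is enzyme elevation.

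**Working it through.** **Rules.** Let *a* be ALT or AST and *b* be bilirubin, both in multiples of ULN in the same sample.

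- Literal reading (elevation means *b* > 1.0): (*a* > 5 and *b* ≤ 1.0) or (*a* > 2.5 and *b* > 1.5)
- Paired reading (elevation means the one named in the second criterion): (*a* > 5 and *b* ≤ 1.5) or (*a* > 2.5 and *b* > 1.5)
- Proposed: *a* > 5 or (*a* > 2.5 and *b* > 1.5)

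**Coverage.** Take a grid in steps of 0.1, with *a* from 0.1 to 20.0 and *b* from 0.1 to 5.0. Above 5x there are 150 enzyme steps (5.1 to 20.0) at each of 50 bilirubin levels, so 150 × 50 = 7,500 points.

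| Bilirubin (x ULN) | Literal | Paired | Proposed |
|---|---|---|---|
| 1.0 | 150 of 150 | 150 of 150 | 150 of 150 |
| each of 1.1, 1.2, 1.3, 1.4, 1.5 | 0 of 150 | 150 of 150 | 150 of 150 |
| 1.6 | 150 of 150 | 150 of 150 | 150 of 150 |

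The literal reading leaves 5 × 150 = 750 points uncovered; the other two leave none. Over the whole grid, the proposed rule adds those 750 points to the literal rule and removes none. These counts show the shape of the gap, not how often it occurs.

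**Hy's Law values.** Appendix C quotes aminotransferase ≥3x ULN with bilirubin ≥2x ULN. Both exceed the cut-offs of the second criterion (2.5x and 1.5x), so no such point is missed.

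**Raised baseline ALT/AST.** For these patients the 7.6.2 thresholds are the only numeric trigger. Of the 7,500 points above 5x, the literal wording covers 7,500 − 750 = 6,750 and the proposed wording 7,500. Copying the Appendix C baseline restriction into 7.6.2 would leave 0.

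**Likely number of cases.** Section 1.3.2 reports drug-related ALT elevation in 13.7% of patients in the phase II NSCLC trial, and Section 15.2 plans 20 patients: 20 × 0.137 = 2.74 with a rise of any size. Let *s* be the share of those falling in the gap. The documents do not give *s*, so a range is assumed. Expected cases are 2.74 × *s*, and the chance of at least one is 1 − (1 − 0.137*s*)^20.

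| Assumed *s* | Expected gap cases | Chance of at least one |
|---|---|---|
| 2% | 0.055 | 5.3% |
| 5% | 0.137 | 12.8% |
| 10% | 0.274 | 24.1% |
| 20% | 0.548 | 42.6% |

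The low end is more plausible. Section 1.3.2 says grade 3 enzyme rises were generally seen at 250 mg twice daily or higher and that bilirubin rose with the enzymes in only a few cases. This trial doses 200 mg twice daily (Section 5.1).

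**The case against.** The strongest reply is that the 1.0x cut-off is supplied by the reader. The only bilirubin figure in the definition is 1.5x ULN, in the companion criterion. Read as a pair, without and with that elevation, the two leave no gap above 5x ULN. Criterion 8 of Section 3.1 supports this: it lists bilirubin up to 1.5x IULN under normal organ function. A third reading is also possible. Section 7.6.3 speaks of changes from baseline, so a stable bilirubin of 1.2x ULN might not count as an elevation at all.

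Other provisions also limit the harm:

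- Section 7.6.2 names drug-induced liver injury as an AESI in general terms, and 7.6.1 allows an event to be judged serious as an important medical event.
- Dosing stops under 6.1, and 6.2 requires agreement with the study supporter to restart after more than 14 days.
- Grade 3 to 5 events reach the CRF (7.7).
- Appendix C step 5 may still bring at least weekly liver tests.

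These points reduce the weight of the concern without removing it. Neither gap-free reading is written down, sites may choose differently, and a reporting trigger should not depend on that choice. Two of the backstops rest on judgement, and none restores the automatic report or the 48-hour evaluation. The stated alignment with the dosing rules helps a reader guess the intent, but on the literal wording the two do not align.

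It is also fair to say that the assumed share has no source, and that the 13.7% covers rises of any size in a trial that included 250 mg twice daily. The case count is only a rough bound.

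**Conclusion.** The concern holds as a minor drafting gap in safety reporting. On the plain wording, every sample with ALT/AST above 5x ULN and bilirubin above 1.0 and up to 1.5x ULN falls outside both numeric triggers, in 7.6.2 and in Appendix C. The absence of a bilirubin condition on the grade 3 enzyme rules in 6.1 and 6.4 suggests that this was not intended.

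The conclusion rests on reading an elevation as any value above ULN; on the paired reading the gap disappears. The statement that dosing is interrupted in this band also assumes that a value above 5x ULN is at least grade 3 under CTCAE, which the protocol does not tabulate.

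The loss is confined to the automatic expedited report and 48-hour work-up in a non-serious case. Most likely no patient, or one, of 20 would be affected. The primary endpoint, the sample size and the analyses are unaffected.

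**What to change.** In 7.6.2 and in the Definition part of Appendix C, reword the first criterion to *ALT and/or AST > 5x ULN, regardless of bilirubin*. Leave the second criterion unchanged. A site that already uses the paired reading would see no change, because the proposed rule gives the same result at every enzyme and bilirubin level.

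Do not carry the Appendix C baseline restriction into 7.6.2, since patients with raised baseline ALT/AST would then lose their only numeric trigger.

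The cost is one phrase in two places, plus IRB approval of the amendment at the coordinating centre and any active secondary site (Section 16.0). Detection needs no new test, because ALT, AST and bilirubin are all in the CMP (Section 10.0). Each added case brings an expedited report and the Appendix C work-up: repeat tests including haptoglobin, reticulocytes, CK and LDH, imaging within 48 hours, and further chemistry and viral serology if cholestasis is not confirmed.
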